10.2 Endpoints

Primary endpoint is whether a lesion can be adequately evaluated with OCT within 5 minutes during a standard of care colonoscopy. If the proportion of the patients whose procedure length using an OCT probe during routine colonoscopy is within 5 minutes is greater than 75%, then the feasibility is defined in this study.

Secondary endpoints include:

- AEs related to OCT imaging during routine colonoscopy
- Whether OCT image is successfully captured using machine learning algorithm, coded as “good” or “noisy”. The OCT imaging catheter will be calibrated before each patient study to ensure that the catheter system is working properly. In an in vivo study of the catheter, we expect some images will be distorted due to patient movement, sub-optimal contact with the mucosa, etc. The machine learning algorithm will judge image quality based on number of colonic crypts visualized (see Section 12, Figure 5). We hypothesize that the proportion of good OCT images is greater than 90%.
- Weighted Kappa. Clinical pathology is the gold standard for diagnosis. Diagnosis from both OCT and clinical pathology will be assigned as normal mucosa, hyperplastic polyp, tubular adenoma, sessile serrated adenoma, or colorectal cancer. Based on ex vivo data from [name] lab, we hypothesize that there will be an over 80% agreement rate in this feasibility study.

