Study Description:	Colorectal cancer arises from the mucosal layer of the colon. Current screening is performed by flexible endoscopy, which involves visual inspection of the mucosal lining of the colon and rectum with an optical camera mounted on the endoscope, with abnormal areas being biopsied. This method is somewhat limited in that there are no readily available surface pattern or morphological classification systems with adequate sensitivity or specificity to evaluate extent of submucosal invasion (deep, superficial, or none). Optical coherence tomography (OCT) using pattern recognition is a high-resolution imaging modality. There is currently an unmet need to predict depth of invasion for colonic tumors to decide on applicability of endoscopic (endoscopic submucosal dissection or endoscopic mucosal resection) vs. surgical therapy. Our hypothesis is that OCT will have a higher diagnostic accuracy for determining depth of submucosal invasion compared to existing modalities. We will first aim to assess the procedural feasibility and safety of using an OCT probe during routine colonoscopy with an early feasibility study. This study will identify appropriate modifications to the device and help with development of subsequent clinical study protocols. The eventual goal is to assess the diagnostic accuracy of OCT imaging for predicting depth of invasion of colonic tumors.
Objectives:	
Primary Objective: To demonstrate the procedural feasibility of OCT during routine colonoscopy.
 
Secondary Objective:
 
 • To describe the safety of the OCT probe during routine colonoscopy. • To evaluate the quality of OCT images using a machine learning algorithm. • To explore the diagnosis agreement between OCT imaging and pathology when a lesion is biopsied.
Endpoints:	
Primary Endpoint: Whether a lesion can be adequately evaluated with OCT within 5 minutes during a standard of care colonoscopy.
 
Secondary Endpoints:
 
 • Adverse events related to OCT imaging during routine colonoscopy. • Whether OCT image is successfully captured using machine learning algorithm.

	
 Weighted kappa
Study Population:	Fifty-four adults undergoing standard of care colonoscopy for the evaluation of colonic polyps will be enrolled in this study.
Phase:	N/A

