1.2 Background

1.2.1 Colonoscopy Polyp Detection Rate and Adenoma Detection Rate

Guidelines support performance targets for adenoma detection rate of 25% for a mixed gender population (20% in women and 30% in men). Polyp detection rate (PDR) and adenoma detection rate (ADR) increase with age, with one study showing a PDR/ADR ratio of 16.9%/6.3% for patients in their 20s, 33%/14.0% for patients in their 30s, 43.5%/28.7% for patients in their 40s, 54.3%/38.4% for patients in their 50s, 61.2%/46.2% for patients in their 60s, 68.7%/55.8% for patients in their 70s, and 65.9%/56.1% for patients in their 80s ($P < 0.001$) [1]. Polyp detection rate is relevant for patient selection. Because we want to maximize the chance that a patient will have a polyp (hyperplastic, adenoma, etc.) that OCT can image, inclusion criteria will include age 40 years or older.

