5.2 Study Procedures

After consent, the endoscopist will perform a standard of care colonoscopy. We will enroll 54 participants in the study and expect approximately 40 of these participants to have polyps. If a polyp is found, then OCT will be used to image that polyp. Patients with polyps, regardless of number found, will have either one tubular adenoma (NICE type 2) imaged OR one hyperplastic polyp (NICE type 1) imaged. These polyps can be distinguished endoscopically using the NICE classification (see Section 12, Figure 1). If no polyps are found, then one area of normal mucosa will be imaged. We will have a goal of imaging an equal number of tubular adenomas and hyperplastic polyps. We will have a running log of the number of imaged tubular adenomas and hyperplastic polyps imaged to ensure that equal amounts of each type are imaged. If on the rare chance a malignant appearing colonic tumor (NICE type 3) is found, this and no other polyps will be imaged with OCT.

Duration of using OCT probe as well as duration of the colonoscopy will be kept by endoscopy staff with a stopwatch. Initiation of colonoscopy will be time 00:00. There will then be time marks for initiation of OCT imaging, end of OCT imaging, and end of colonoscopy. In this way, the exact duration of OCT and the full duration of colonoscopy with OCT will be captured.

Duration of OCT imaging will be from the time of guiding the OCT probe through the colonoscope to imaging, and withdrawal of OCT probe. The maximum time allotted to obtain OCT imaging will be 10 minutes. Any OCT imaging that reaches the 10-minute mark will be stopped so that routine colonoscopy can resume. A log of total procedure duration is kept for every standard of care colonoscopy.

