5.3 Definitions of Evaluability

A patient must have had at least one colonic polyp or area of normal mucosa selected for OCT imaging in order to be evaluable for the feasibility endpoint. Any patient who does not have any area of mucosa imaged by OCT (either due to poor bowel prep, anesthesia complications, etc.), will be considered inevaluable for the feasibility endpoint and will be replaced.

All patients who undergo colonoscopy using the OCT probe are evaluable for toxicity and evaluation of imaging quality. Patients are evaluated for AEs from time of colonoscopy until 48 hours after colonoscopy.

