10.3 Sample Size Calculation

The sample size calculation is based on the primary endpoint of feasibility only. The primary hypothesis is that the proportion of the patients who have OCT imaging which adds 5 minutes or less to the duration of standard of care colonoscopy is greater than 75%. The null hypothesis for feasibility is 75% and the alternative hypothesis is 90%. $H_0: p < 75\%$ $H_a: p > 75\%$ (expect it to be 90% in clinical practice). A sample size of 54 patients achieves 80.1% power to detect a difference of 15% using a two-sided exact test at a significance level of 5% with the assumption that the proportion is 75%.

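### The primary endpoint is worded as adequate evaluation of a lesion, but the feasibility rule scores time only and counts patients imaged only on normal mucosa

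*Combined protocol and SAP*

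**What the plan says.** The Protocol Summary and Section 2.0 give the primary endpoint as "Whether a lesion can be adequately evaluated with OCT within 5 minutes during a standard of care colonoscopy", and Section 10.2 repeats it: "Primary endpoint is whether a lesion can be adequately evaluated with OCT within 5 minutes during a standard of care colonoscopy". No section says what makes an evaluation adequate.

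The next sentence of 10.2 gives the decision rule: "If the proportion of the patients whose procedure length using an OCT probe during routine colonoscopy is within 5 minutes is greater than 75" per cent, feasibility is met. Section 10.3 powers "the proportion of the patients who have OCT imaging which adds 5 minutes or less to the duration of standard of care colonoscopy", with a null rate of 75%, an expected rate of 90%, 54 patients, a two-sided exact test at 5% and a stated power of 80.1%. Section 5.2 defines the time itself: "Duration of OCT imaging will be from the time of guiding the OCT probe through the colonoscope to imaging, and withdrawal of OCT probe".

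On who is counted, Section 5.2 states: "We will enroll 54 participants in the study and expect approximately 40 of these participants to have polyps". The others have an area of normal mucosa imaged. Section 5.3 makes both groups evaluable for feasibility: "A patient must have had at least one colonic polyp or area of normal mucosa selected for OCT imaging in order to be evaluable".

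Image quality (coded *good* or *noisy*) and weighted kappa against pathology are secondary endpoints in 10.2. Section 10.5.4 gives each a 95% confidence interval.

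**The concern.** The endpoint as worded has three parts: a lesion, adequately evaluated, within 5 minutes. The rule that decides the trial uses only the third. A site scanned in 3 minutes and coded *noisy* is a primary success, and so is a quick scan of normal mucosa in a patient without a polyp. Noisy scans are not a remote case, since 10.2 itself expects some images to be distorted by movement or poor contact.

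Section 1.1 makes a later study in large complex polyps conditional on this one succeeding. That next step concerns lesions, yet no on-time proportion is planned for polyp patients alone. The plan also does not say whether success means an observed proportion above 75% or rejection by the exact test.

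**Working it through.** **Inputs.** From 10.3: n = 54, p0 = 0.75, p1 = 0.90, two-sided 5%, exact test. From 5.2: about 40 patients with polyps, hence 54 − 40 = 14 (26%) on normal mucosa only. On-time rates by site type are not given; any used below are assumptions.

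**1. The plan's own power.** The normal approximation, with null variance for the cut-off and alternative variance for power, is

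Φ{[0.15 − 1.96·√(0.75·0.25/54)] / √(0.90·0.10/54)} = Φ{(0.15 − 0.1155)/0.0408} = Φ(0.845) = 0.801.

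This reproduces 80.1%. The exact binomial power is 83.2%, so the stated figure is an approximation that errs on the cautious side. Either way, it is power for time only, in all 54 patients.

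**2. Two possible pass marks.**

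| Reading | Smallest passing count | Chance of passing at a true 75% | Exact 95% CI at that count |
|---|---|---|---|
| Observed proportion above 75% (10.2, literal) | 41/54 = 75.9% | 0.511 | 62.4% to 86.5% |
| Exact test (10.3) | 47/54 = 87.0% | 0.024 | 75.1% to 94.6% |

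One fewer, 46/54, has an upper tail of 0.0525 and a lower limit of 72.9%, so 47 is the critical value.

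**3. What a pass implies for polyps.** With 40 polyp and 14 normal-mucosa patients, the polyp successes needed equal the pass mark minus the normal-mucosa successes.

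- All 14 normal-mucosa patients on time: 41 − 14 = 27/40 (67.5%) meets the literal rule, and 47 − 14 = 33/40 (82.5%) passes the exact test.
- 13 of 14 on time: 28/40 (70.0%) and 34/40 (85.0%).
- 9 of 14 on time: the exact test needs 47 − 9 = 38/40 (95.0%).

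So the same verdict can go with quite different polyp results, in either direction.

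**4. Pooling, as illustration only.** Let polyps be on time at a true 75% and normal mucosa at an assumed rate q. The number on time is Bin(40, 0.75) + Bin(14, q).

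| q | 65% | 75% | 85% | 90% | 100% |
|---|---|---|---|---|---|
| P(47 or more of 54) | 0.8% | 2.4% | 6.0% | 8.9% | 18.2% |

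These are not type I errors of the plan's hypothesis, which concerns the pooled rate. At q = 100%, for example, the pooled rate is (30 + 14)/54 = 81.5%, already above 75%.

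**5. How firm is 14?** Section 1.2.1 cites polyp detection rates of "43.5%/28.7% for patients in their 40s, 54.3%/38.4% for patients in their 50s, 61.2%/46.2% for patients in their 60s, 68.7%/55.8% for patients in their 70s". Applied to 54 patients, 43.5% to 68.7% gives about 23 to 37 with polyps and 17 to 31 on normal mucosa. The low end would need nearly everyone to be in their forties, and 5.1 also recruits surveillance and prior-polyp patients, so 40 remains possible.

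**The case against.** The best defence is that the rule is prespecified and suits the objective. The objective is procedural feasibility, 1.3.1 names added time as the surrogate for ease of the procedure, and 10.2 and 10.3 state the time criterion openly. That stands, and it is why the powered test should be kept. It does not make the result evidence on the endpoint as worded.

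Second, adequacy is not ignored: image quality and OCT-versus-pathology agreement each have their own analysis. This also stands. A reader might infer that the plan never examines how well OCT evaluates lesions, and the documents do not support that. What remains is that neither analysis can alter the feasibility verdict. Section 10.5.4 names time and image quality in one sentence and could be read as a joint proportion. Its plurals suggest two proportions, and even a joint reading would leave the 10.2 rule and the 10.3 hypothesis time-only.

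Third, a reader might infer that normal-mucosa patients make success easier, or inflate the error rate. The documents do not support this. Inclusion of normal mucosa is stated openly in 1.3.1, 5.2 and 5.3, and 5.2 gives the same steps and expected times for both kinds of site.

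Fourth, the three descriptions of time in 5.2, 10.2 and 10.3 might be read as three different endpoints. Colonoscopy pauses for OCT and then resumes, so they are practically one quantity. Using one wording is a matter of tidiness.

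**Conclusion.** The mismatch between the endpoint's wording and its decision rule is in the text and needs no assumption. A feasible result will show that OCT imaging took 5 minutes or less at the imaged site in enough patients. By itself it will not show that lesions were adequately evaluated.

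The unresolved pass mark is the part with a firm size: 41 or 47 of 54, with a 51% or 2.4% chance of passing at a true 75%. The effect of pooling is unknown in size and direction. The range of 0.8% to 18.2% rests on an assumed 40/14 split, polyps at exactly 75%, and assumed normal-mucosa rates of 65% to 100%.

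This should be corrected before results are seen. It does not invalidate the powered test.

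**What to change.** 1. Keep the time-only test. In the Protocol Summary, 2.0, 10.2 and 10.3, word the endpoint identically as OCT duration (probe in to probe out, as in 5.2) of 5 minutes or less at the imaged site, whether polyp or normal mucosa. State that feasibility is judged by the exact test: 47 or more of 54, equivalently an exact 95% lower limit above 75%.
2. In 10.5.4, add the on-time proportion separately for polyp and normal-mucosa patients with exact 95% confidence intervals. Rest any statement about lesions on the polyp patients.
3. Optionally, report among polyp patients the proportion both on time and coded *good*, as description only. This needs one rule that turns a site's several hundred images into a patient-level code. Add a caution: the code rests on visible crypts (10.2), and 1.2.3 uses a structural pattern as a marker of normal tissue, so well-imaged neoplastic tissue may be coded *noisy*. The code should therefore not be compared between polyps and normal mucosa as a measure of image quality. Do not claim adequate evaluation from time alone.

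**Cost.** Wording in four places, one sentence on the pass mark, and a few descriptive proportions from the stopwatch times, imaging record and image code; no extra patients. The downside is precision. With 40 polyp patients the exact test needs 36 on time and has about 63% power for 75% versus 90%, and 32/40 would have a 95% confidence interval of 64% to 91%. The split should be labelled descriptive, with the stated power applying only to the pooled test.

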10.5.4 Endpoint Analysis

Proportions of the patients whose procedure length using an OCT probe during routine colonoscopy is within 5 minutes and who have good OCT images, as judged by a machine learning algorithm, will be provided. Their associated 95% confidence intervals (CIs) will be calculated assuming a binomial distribution. The descriptive statistics will be presented including frequency, type, and severity of AEs related to OCT imaging during routine colonoscopy. Weighted kappa and 95% CI will be computed for the agreement between OCT imaging and pathology for all enrolled patients. All analyses will be conducted using SAS (SAS Institute, Cary, NC) at the two-sided 5% significance level.

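### Feasibility is declared when the proportion exceeds 75%, the null value itself: 41 of 54 suffices, with 51% error at a true rate of 75%, while the exact test behind the sample size needs 47 of 54

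*Combined protocol and SAP*

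**What the plan says.** Three sections of the combined protocol and SAP bear on how the primary endpoint is decided.

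- **10.2 Endpoints** gives the only if-then rule. If the proportion of patients whose OCT procedure length "is within 5 minutes is greater than 75%, then the feasibility is defined in this study". It mentions no test, p-value or confidence limit.
- **10.3 Sample Size Calculation** takes 75% as the null value and 90% as the alternative ("expect it to be 90% in clinical practice"). It states: "A sample size of 54 patients achieves 80.1% power to detect a difference of 15% using a two-sided exact test", at the 5% level.
- **10.5.4 Endpoint Analysis** says that the proportions within 5 minutes and with good images will be given. It adds: "Their associated 95% confidence intervals (CIs) will be calculated assuming a binomial distribution". It closes with a general two-sided 5% level for all analyses. It names no test of 75%, does not say which binomial interval is meant, and attaches no success criterion to the interval.

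Section 5.3 replaces patients who cannot be evaluated for feasibility, so 54 is the evaluable denominator.

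**The concern.** The success cut-off in 10.2 equals the null value in 10.3. A rule that passes whenever the estimate lies above the null value passes about half the time when the null value is the truth. The 5% significance level and the power in 10.3 belong to a different and much stricter rule, and nothing in 10.5.4 connects the two.

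Section 1.1 makes the follow-on accuracy study, in patients with large complex polyps, conditional on this study succeeding. With 43 of 54, say, one reader could cite 10.2 and declare feasibility while another cites 10.3 and declares failure. That choice should not be open once the data are known.

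The stated power also needed checking, because 80.1% did not look like the power of an exact test at this sample size.

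**Working it through.** **Inputs.** From 10.3: n = 54, p0 = 0.75, p1 = 0.90, two-sided exact test, alpha 0.05, stated power 80.1%. From 10.2: success if the proportion is above 0.75. X is the number of patients within 5 minutes, taken as binomial(54, p).

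**1. The plan's own power figure.** The two-sided one-sample z-test, with the null variance and no continuity correction, gives

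power = Φ[(0.15·√54 − 1.96·√(0.75·0.25)) / √(0.90·0.10)]
= Φ[(1.1023 − 0.8487) / 0.3000]
= Φ(0.845) = 0.801.

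This reproduces 80.1%, so the figure comes from a normal approximation.

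**2. The test that 10.3 names.** An exact test with at most 2.5% in each tail:

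- Upper tail: P(X ≥ 46 | 0.75) = 0.0525, too large; P(X ≥ 47 | 0.75) = 0.0241. Success needs X ≥ 47 (87.0%).
- Lower tail: P(X ≤ 33 | 0.75) = 0.0169. Actual two-sided size = 0.0241 + 0.0169 = 0.0410.
- Power: P(X ≥ 47 | 0.90) = 0.832.

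Ordering outcomes by likelihood instead of using equal tails also gives 47 as the upper cut-off and 0.832 as the power.

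**3. The rule in 10.2.** 40/54 = 74.1% fails and 41/54 = 75.9% passes, so the rule is X ≥ 41.

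| True p | Declared feasible under 10.2 (X ≥ 41) | Success on the exact test (X ≥ 47) | Rules disagree (X = 41 to 46) |
|---|---|---|---|
| 0.70 | 21.4% | 0.3% | 21.1% |
| 0.75 | 51.1% | 2.4% | 48.6% |
| 0.80 | 82.3% | 12.8% | 69.4% |
| 0.85 | 97.4% | 42.7% | 54.8% |
| 0.90 | 99.9% | 83.2% | 16.7% |

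**4. What the planned interval would show.** At 41/54 the exact 95% CI is 62.4% to 86.5%, so a result that 10.2 calls feasible is compatible with rates well below 75%. At 47/54 it is 75.1% to 94.6%.

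**5. Why the type of interval must be named.** 10.5.4 says only that the interval is binomial. At 46/54 the lower limits are:

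- exact (Clopper-Pearson): 72.9%, fails
- Wilson: 73.4%, fails
- Wald: 75.7%, passes

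Under a Wald interval 46 would succeed, with an upper-tail error at p = 0.75 of 5.25%, about twice the 2.5% that a two-sided 5% test allows.

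**The case against.** The best defence is that 10.2 loosely restates the alternative hypothesis. The word observed does not appear there, and 10.3 puts its hypothesis about the proportion in very similar terms. Taken together, 10.3 supplies a test and a null value, and 10.5.4 supplies a 5% level and a 95% interval, so all that is missing is a linking sentence. This reading is possible but not the natural one, because 10.2 states an if-then rule for this study. Even if it is accepted, no section says what decides feasibility, and the same edit is needed.

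Several narrower points do stand:

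- The 51% applies at p = 0.75 exactly, the worst case under the null. It falls to 21.4% at 0.70, 5.9% at 0.65 and 1.1% at 0.60.
- The power error is conservative. The exact test does better than stated, and 54 patients are enough for it.
- The plan does not say it will use a Wald interval. The example shows only that the method should be fixed.
- The higher bar has a price if a point-estimate rule was what the sponsor wanted. At a true rate of 80% the chance of success falls from 82% to 13%, and at 85% from 97% to 43%. How much certainty an early feasibility study needs is partly a design judgement. Section 10.3 has already made that judgement by choosing a null, an alternative, an alpha and a power.

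**Conclusion.** The concern holds, and the rule should be corrected before any data are seen. On its natural reading, 10.2 declares feasibility from 41 of 54 upward, with a 51.1% chance of doing so at a true rate of 75%. The test used to size the trial needs 47 of 54, with an upper-tail error of 2.4%. The six results from 41 to 46 lead to opposite conclusions in the two sections. Such a result has a probability of 49% if the true rate is 75% and 69% if it is 80%.

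These figures assume 54 evaluable patients with independent outcomes and a common success rate. The 51.1% also assumes that 10.2 refers to the observed proportion; otherwise the defect is a missing success criterion.

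The mislabelled power (80.1% stated, 83.2% for the exact test) is secondary and does not affect the adequacy of the sample size.

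**What to change.** - **10.2 and 10.5.4:** state that feasibility is declared if the lower limit of the exact (Clopper-Pearson) two-sided 95% CI for the proportion exceeds 75%, which with 54 evaluable patients means at least 47 successes. Name the interval method in 10.5.4.
- **10.3:** restate the power as 83.2% at a true rate of 90%, with an actual two-sided size of 4.1%, or label 80.1% as a normal-approximation figure.

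The cost is wording in three sections and no additional patients. The bar rises from 41 to 47 of 54, which is the bar that the exact test in 10.3 already implies. If the sponsor prefers to keep a point-estimate rule, the plan should say so openly, give its error rate (51.1% at a true rate of 75%), and stop attaching the 5% level and the stated power to it.

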2.0 OBJECTIVES AND ENDPOINTS

Objectives	Endpoints
Primary	
To demonstrate the procedural feasibility of OCT during routine colonoscopy	Whether a lesion can be adequately evaluated with OCT within 5 minutes during a standard of care colonoscopy.
Secondary	
To describe safety of OCT probe during routine colonoscopy	Adverse events related to OCT imaging during routine colonoscopy
To evaluate the quality of OCT images using a machine learning algorithm.	Whether OCT image is successfully captured using machine learning algorithm
To explore the diagnosis agreement between OCT imaging and pathology when a lesion is biopsied.	Weighted kappa

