Surface pattern	· Regular dark or white spots · Similar to surrounding normal mucosa	· Regular (tubular/branched/papillary)	· Irregular or obscure	· Amorphous areas
Most likely histology	Hyperplastic polyp/ Sessile serrated polyp	Low grade intramucosal neoplasia	High grade intramucosal neoplasia/ Shallow ^{※3} submucosal invasive cancer	Deep submucosal invasive cancer
Endoscopic image				

*1. If visible, the caliber in the lesion is similar to surrounding normal mucosa.

*2. Microvessels are often distributed in a punctate pattern and well-ordered reticular or spiral vessels may not be observed in depressed lesions.

*3. Deep submucosal invasive cancer may be included.

Figure 4. JNET classification.

[figure not shown]

Figure 5. OCT imaging of normal colon tissue and colon cancer on left, corresponding pathology on right.

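### Weighted kappa is the only endpoint for OCT-pathology agreement, but the three polyp types have no agreed order and the plan fixes neither order nor weights

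*Combined protocol and SAP*

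**What the plan says.** The third secondary objective (Section 2.0) reads: "To explore the diagnosis agreement between OCT imaging and pathology when a lesion is biopsied". Its endpoint is given, there and in the Protocol Summary, simply as weighted kappa.

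Section 10.2 makes clinical pathology the reference and names the categories: "Diagnosis from both OCT and clinical pathology will be assigned as normal mucosa, hyperplastic polyp, tubular adenoma, sessile serrated adenoma, or colorectal cancer". It adds an expectation based on ex vivo data: "we hypothesize that there will be an over 80% agreement rate in this feasibility study". That is a raw proportion, not a kappa value.

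Section 10.5.4 gives the analysis: "Weighted kappa and 95% CI will be computed for the agreement between OCT imaging and pathology for all enrolled patients". It plans no raw agreement proportion and no unweighted kappa.

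On numbers, Section 5.2 states: "We will enroll 54 participants in the study and expect approximately 40 of these participants to have polyps". On the mix of lesions it states: "We will have a goal of imaging an equal number of tubular adenomas and hyperplastic polyps". Where no polyp is found, one area of normal mucosa is imaged.

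The documents nowhere declare the five diagnoses ordinal, say that the order in Section 10.2 is a scoring order, or specify linear, quadratic or other weights.

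**The concern.** Weighted kappa gives partial credit for near misses, so someone must decide which misses are near. That is straightforward for grades of one condition. Here the categories are types. Most polyp data will fall into hyperplastic polyp, tubular adenoma and sessile serrated adenoma, and more than one order of these three can be argued.

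With order and weights left open, the endpoint cannot be computed from the plan as it stands. The choice would be made later, possibly with the cross-table in view, and the same OCT readings could be reported as different levels of agreement. The one stated expectation, agreement over 80%, also has no matching analysis, because weighted kappa does not estimate that proportion.

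**Working it through.** The plan states no kappa value, so there is no figure to reproduce. The check is whether one fixed table gives different kappas when only the order or the weights change.

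**Inputs from the documents.** Five categories (Section 10.2), about 40 participants with polyps out of 54 (Section 5.2), and an agreement rate around 80% (Section 10.2).

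**Assumed, because the documents give no cell counts.** The tables below, each with 40 lesions and 8 errors, so raw agreement is 32/40 = 80%. HP = hyperplastic polyp, TA = tubular adenoma, SSA = sessile serrated adenoma. Cells are pathology to OCT.

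- Table A, all errors HP/SSA: HP-HP 13, HP-SSA 4, TA-TA 17, SSA-SSA 2, SSA-HP 4. Both margins are 17, 17, 6.
- Table B, all errors HP/TA: HP-HP 14, HP-TA 4, TA-TA 14, TA-HP 4, SSA-SSA 4. Both margins are 18, 18, 4.
- Table C, mixed errors: HP-HP 15, HP-TA 2, HP-SSA 1, TA-TA 15, TA-HP 2, TA-SSA 1, SSA-SSA 2, SSA-HP 1, SSA-TA 1. Both margins are 18, 18, 4.
- Table A with 14 correctly read normal areas added: 54 − 40 = 14, so n = 54 and agreement is 46/54 = 85%.

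**Formula.** Kappa = 1 − O/E, where O is the sum of d × observed count and E is the sum of d × (row total × column total / n). The disagreement weight d between positions i and j is |i−j|/4 (linear), (|i−j|/4)² (quadratic), or 1 for any error (unweighted).

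**Orders compared.** Listed: normal, HP, TA, SSA, cancer. Swapped: normal, HP, SSA, TA, cancer.

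**Table A in full.**

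- Unweighted: O = 8; E = (1600 − 289 − 289 − 36)/40 = 24.65; kappa = 0.68.
- Listed, linear: O = 8 × 2/4 = 4; E = (578 × 1/4 + 204 × 2/4 + 204 × 1/4)/40 = 297.5/40 = 7.44; kappa = 0.46.
- Swapped, linear: O = 8 × 1/4 = 2; E = (578 × 2/4 + 204 × 1/4 + 204 × 1/4)/40 = 391/40 = 9.78; kappa = 0.80.
- Listed, quadratic: O = 8 × 4/16 = 2; E = 99.875/40 = 2.50; kappa = 0.20.
- Swapped, quadratic: O = 8 × 1/16 = 0.5; E = 170/40 = 4.25; kappa = 0.88.

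**All tables by the same steps.**

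| Table | Unweighted (any order) | Linear, listed | Linear, swapped | Quadratic, listed | Quadratic, swapped |
|---|---|---|---|---|---|
| A: HP/SSA errors | 0.68 | 0.46 | 0.80 | 0.20 | 0.88 |
| B: HP/TA errors | 0.66 | 0.70 | 0.60 | 0.77 | 0.56 |
| C: mixed errors | 0.66 | 0.63 | 0.70 | 0.59 | 0.72 |
| A plus 14 normal areas | 0.79 | 0.72 | 0.89 | 0.69 | 0.95 |

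The direction depends on which types OCT confuses: the listed order gives the lower value in A and C and the higher value in B. If neither OCT nor pathology uses the sessile serrated category and only HP and TA occur, the table is 2 × 2 and the choice makes no difference. With 20 of each type and 4 errors each way, every version gives 0.60.

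**The case against.** The strongest reply is that weighted kappa accepts any weight matrix, and that Section 10.2 only lists diagnoses without calling the list a scale. This is correct. A reader might infer that the plan will score in the listed order, and so count hyperplastic versus sessile serrated as a two-step error. The documents do not say so. The point that stands is that order and weights are unspecified.

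A reader might also use the JNET table (Section 12.0, Figure 4), which places "Hyperplastic polyp/ Sessile serrated polyp" in one type, to argue that these two diagnoses must be adjacent. That goes too far. JNET is background in Section 1.2.2 and groups lesions by endoscopic vessel and surface pattern. Section 5.2 selects polyps by NICE. Neither settles which OCT-pathology confusion is closest.

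Table A alone would suggest that the same data can always read as poor or as excellent. It is close to a worst case in one direction. Section 5.2 aims for equal numbers of tubular adenomas and hyperplastic polyps and does not select for sessile serrated lesions. Table B reverses the effect and Table C shrinks it. Correctly read normal areas narrow it, although they enter only if they have pathology.

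Finally, it might be inferred that the weighting undermines the follow-on study. Section 1.1 makes that study conditional on feasibility and directs it at depth of submucosal invasion, which a five-type kappa does not measure under any weights. Section 1.3.2 calls the pathology comparison exploratory, Section 10.3 sizes the trial on feasibility alone, and no decision rests on a kappa threshold.

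It can also be said that fixing the weights in advance would be enough. That would make the endpoint computable, but it would still rest on an order that is open to dispute. Unweighted kappa avoids the dispute.

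**Conclusion.** The concern holds as a weakness in the choice and specification of a secondary, exploratory endpoint. In the assumed 40-lesion tables at 80% agreement, swapping two polyp types changes linear kappa by 0.34 (Table A), 0.10 (B) or 0.07 (C), and quadratic kappa by 0.68, 0.21 or 0.13, computed from the rounded values above. The direction is not constant. With the 14 normal areas added to Table A, the changes are 0.17 and 0.26. With few or no sessile serrated lesions the effect can be small or absent.

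These sizes rest on assumed cell counts. The dependence on order and weights follows from the statistic itself whenever three or more unordered types are in use. The primary feasibility conclusion is unaffected.

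**What to change.** In the Protocol Summary and Sections 2.0, 10.2 and 10.5.4, replace weighted kappa with unweighted (Cohen's) kappa and its 95% CI. Report with it:

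- the full OCT-by-pathology cross-table;
- raw agreement with a 95% CI, which is the quantity the over-80% hypothesis refers to;
- agreement within each pathology class.

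If a weighted version is kept, make it a sensitivity analysis. Write down and justify the weight matrix before any OCT diagnosis is compared with pathology.

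The cost is wording in four places, with no new data, participants or procedures. The small downside is that unweighted kappa gives no credit for near misses and counts a normal/cancer error like any other. The full table makes such errors visible.
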